5. INTRODUCTION AND BACKGROUND

The study will be conducted in accordance with ethical principles that have their origin in the Declaration of Helsinki and in compliance with the protocol, Good Clinical Practice (GCP) and all applicable regulations.

5.1 Background

[figure not shown]
The purpose of this study is to assess the safety and effectiveness of using IC2000 and SPY-PHI as an intraoperative fluorescence visualization tool of lymphatic vessels and identification of lymph nodes (histology confirmed LN detected by IC2000 and SPY) during lymphatic mapping and sentinel lymph node biopsy (SLNB) in subjects with early stage breast cancer.

[figure not shown]

[figure not shown]
5.1.1 Breast Cancer

[figure not shown]

[figure not shown]

[figure not shown]

[figure not shown]

5.2 Potential Risks and Benefits to Human Subjects

In this study, IC2000 and SPY-PHI will be assessed as an intraoperative fluorescence visualization tool in the identification of lymphatic vessels and lymph nodes (histology confirmed LNs detected by IC2000 and SPY-PHI) during lymphatic mapping in subjects undergoing sentinel lymph node biopsy with early stage breast cancer.

The device does not have diagnostic capabilities. The surgeon / user retains the ultimate responsibility for making the pertinent diagnosis based on their standard practice and visual comparison of the separate images obtained.

SPY-PHI is classified by the United States FDA as a Class II medical device with a Product Code of OWN. SPY-PHI has a 510(k) clearance from the FDA (K200737) for the following indications for use:

"Upon intravenous administration of SPY AGENT™ GREEN (indocyanine green for injection, USP) the SPY-PHI System is used with SPY AGENT™ GREEN to perform intraoperative fluorescence angiography. The SPY-PHI System is indicated for use in adult and pediatric patients one month of age and older.

The SPY-PHI System is indicated for fluorescence imaging of blood flow and tissue perfusion before, during, and after: vascular, gastrointestinal, organ transplant, and plastic, micro- and reconstructive surgical procedures.

Upon interstitial administration of SPY AGENT™ GREEN, the SPY-PHI System is used to perform intraoperative fluorescence imaging and visualization of the lymphatic system, including lymphatic vessels and lymph nodes."

SPY-PHI is also licensed in Canada as a class 2 medical device with the following intended use:

[figure not shown]
Upon intravenous administration of SPY AGENT™ GREEN (Indocyanine green for injection, USP) the SPY-PHI System is used with SPY AGENT™ GREEN to perform intraoperative fluorescence angiography.

The SPY-PHI System is indicated for fluorescence imaging of blood flow and tissue perfusion before, during, and after: vascular, gastrointestinal, organ transplant, and plastic, micro- and reconstructive surgical procedures.

Examples of its use for near-infrared fluorescence imaging before, during and after various procedures include, but are not limited to, coronary bypass surgery, organ transplant procedures, plastic and reconstructive surgery such as breast reconstructive procedures and micro-surgery (including plastic reconstructive surgery utilizing autologous flaps), renal cancer surgeries, vascular surgeries (such as wound, amputation and coronary vessels), myocardial perfusion in cardiac and cardiovascular surgeries, GI surgeries and parathyroid perfusion during endocrine surgery.

The risks of the SPY-PHI system in humans are described further in Section 11, Risks / Precautions. For detailed information, please refer to the SPY-PHI Operator's Manual³⁸.

The imaging agent ICG, is approved for use in humans by the FDA and Health Canada. In this study, investigational ICG (IC2000) will be administered intradermally and used with SPY-PHI as an intraoperative fluorescence visualization tool in the identification of

These and other risks of ICG in humans are described further in Section 11, Risks/Precautions. For additional information, please refer to the commercial ICG Package Insert 45.

6. STUDY OBJECTIVES

6.1 Objectives

Primary

 To assess the effectiveness of IC2000 and SPY-PHI (SPY Portable Handheld Imager; also called "IC2000 and SPY") Fluorescence Imaging System in the identification of lymph nodes (histology confirmed lymph nodes), during lymphatic mapping and sentinel lymph node biopsy in subjects with early stage breast cancer.

Secondary

- To evaluate the effectiveness of IC2000/SPY and Tc99m/Gamma Probe in the identification of at least one lymph node (histology confirmed lymph node) per subject.
- To evaluate the effectiveness of IC2000 and SPY as an intraoperative fluorescence visualization tool in delineation and mapping of lymphatic vessels in the identification of lymph nodes (histology confirmed lymph nodes).
- To confirm the safety of intradermal injection of IC2000 in intraoperative delineation and mapping lymphatic vessels and identification of lymph nodes.

7. INVESTIGATIONAL PLAN

7.1 Study Design Overview

This is a prospective, open label, multicenter, non-inferiority within-patient study to determine the effectiveness of IC2000 (Indocyanine Green (ICG) for Injection) and the SPY Portable Handheld Imaging System (SPY-PHI), as an intraoperative fluorescence visualization tool in the visual identification of lymphatic vessels and identification of LNs during lymphatic mapping and SLNB procedures as confirmed by Tc99m and Gamma

Probe. Enrollment will not exceed 190 subjects at up to 10 centers in North America. Prior to enrolling study subjects, participating surgeons at each center will be:

- Required to have completed a minimum of (5) lymphatic mapping and sentinel lymph node identification procedures using SPY-PHI with ICG.
- Trained to perform the intradermal injection technique using ICG.

7.2 Screening

Subjects diagnosed with breast cancer with either Ductal Carcinoma in Situ (DCIS) (Stage 0, Tis, N0, M0) or clinical stage IA, IB or IIA who are scheduled for surgery that includes clinically indicated SLNB with Tc-99m radioactive colloid and Gamma Probe (Note: Only subjects who subsequently consent to undergo LN mapping and identification using IC2000 and SPY-PHI as an intraoperative fluorescence visualization tool may be enrolled in the study).

Subjects will be evaluated at baseline to determine if they meet the inclusion/exclusion criteria of the FILM-B protocol. Subjects considered for inclusion in the study will be assessed to determine overall health status including demographics, vital signs, diagnosis and relevant medical history/underlying conditions.

7.3 Day 0

Eligible subjects who have provided informed consent will be enrolled in the study on Day 0. The surgical procedure will be performed according to the surgeons and/or institutions standard practice.

7.3.1 Intraoperative Lymphatic Mapping and Lymph Node Identification

As per standard of care, all subjects will receive an injection of Tc-99m radioactive colloid either the day before or the morning of surgery². On the day of surgery subjects will receive an injection of IC2000 at the start of surgery while the subject is in the operating room and under anesthesia. The injection will occur prior to SLNB as IC2000 and SPY will be used to map and identify LNs for excision.

The breast(s) identified with DCIS or stage IA, IB or IIA cancer will be injected with IC2000 (2.5 mg/ml solution) in the peri-areolar area as described below.

[figure not shown]
7.4 Classification of LNs

7.5 Follow-up and Post-operative Complications

All subjects will have standard of care assessments throughout the study according to the hospitals/institution's standard procedures. Study specific visits will monitor the occurrence of any adverse events/adverse device effects (AEs/ADEs) on the date of discharge and Day 30 (±7 days). All adverse events will be followed up to Day 30 (±7 days). Adverse events thought to be related to the use of IC2000, SPY, Tc-99m radioactive colloid, or to the LN mapping procedure will be followed until resolution or deemed chronic. In addition, all concomitant medications will be recorded if taken to treat an AE, ADE, Serious AE (SAE) or unanticipated ADE (UADE).

The overall study design is shown below in Figure 1.

8. SELECTION AND WITHDRAWAL OF SUBJECTS

8.1 Number of Subjects

Enrollment in the study will not exceed

8.2 Inclusion Criteria

To be eligible for the study, a subject must meet all of the following criteria:

- 18 years of age or older.
- Subjects with American Cancer Society Clinical Stage 0 Ductal Carcinoma in Situ (DCIS) (Stage 0, T_{is}, N0, M0), IA (T1*, N0, M0), IB ((T0, N1mi, M0) or T1*, N1mi, M0)) or Stage IIA (T0, N1**M0, or T1, N1**, M0 or T2, N0, M0)1 breast cancer undergoing surgery to remove tumor draining LNs.

Where:

- T_{is} = Ductal carcinoma in situ
- T0 = No evidence of primary tumor
- T1 = Tumor ≤ 20 mm in greatest diameter
- T1* = Includes T1mi
- T2 = Tumor >20 mm but ≤ 50 mm in greatest diameter
- N0 = No regional lymph node metastasis
- N1 = Metastasis to movable ipsilateral level I, II axillary LNs
- N1** = T0 and T1 tumors with nodal micro-metastasis only are excluded from Stage IIA and are classified Stage IB.
- mi = Micro-metastasis
- M0 = Disease has not metastasized
- Subjects with clinically negative nodal status (N0) with or without neoadjuvant therapy.
- Subjects with negative metastatic involvement (M0).
- Subjects of child-bearing potential must not be pregnant or lactating and must have a negative pregnancy test at Baseline.
- Have signed an approved informed consent form for the study.
- Be willing to comply with the protocol.

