9. SUBJECT ENROLLMENT AND SUBJECT IDENTIFICATION PROCEDURES

9.1 Subject Enrollment

Enrollment will occur on the day of surgery. Prior to surgery, the subject will have provided written informed consent, completed all baseline procedures and met all the requirements of inclusion and exclusion. Enrollment should be performed as closely as possible to the surgical procedure to minimize the incidence of dropout. Enrollment is completed only after verification of proper informed consent and study eligibility.

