9.1.1 Subject Enrollment Procedure

Since this study is a single arm design, randomization is not required. In the FILM-B study, each subject will serve as their own control. All subjects enrolled will receive the same study treatment, which is lymphatic mapping using IC2000/SPY-PHI and Tc99/Gamma Probe during sentinel lymph node biopsy. This will allow for a direct, non-inferiority comparison of IC2000 and SPY-PHI to Tc99 and Gamma Probe in lymphatic mapping and identification of LNs during SLNB in subjects with early stage breast cancer. The study coordinator or designee will verify that the subject is eligible and that informed consent has been obtained prior to initiating the enrollment process. Once complete, the study coordinator or designee will assign the subject an Enrollment ID Number and the subject will be considered enrolled in the trial. The study coordinator will then disclose to the Investigator that the enrollment process is complete.

A subject cannot receive study treatment until the enrollment process has been completed. The enrollment procedure should not be initiated unless the study coordinator or designee verifies the baseline information and confirms that the subject is eligible. If any deviations occur (errors such as assigning incorrect enrollment), the clinical site will be required to contact the Sponsor and wait for guidance on how to proceed.

If, at any time after enrollment, the subject becomes ineligible or withdraws, the subject will be categorized with respect to the definitions outlined for the analysis populations (see Section 14, Statistical Methods).

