12.3 Day 0 Procedures

As per standard of care, all subjects will receive an injection of Tc-99m either the day before or the morning of surgery.

Subjects are considered enrolled after verification of proper informed consent and eligibility, just prior to the time of injection of IC2000, at the start of surgery while the subject is in the operating room and under anesthesia (see below for administration procedures).

For mapping procedure details, refer to Section 7.3.1.2, Visual Identification and Mapping Procedure.

All subjects will undergo the appropriate surgical procedure according to the surgeons and/or hospitals standard practice for breast cancer surgery. The surgical procedures will include either a lumpectomy or a mastectomy.

[figure not shown]
All subjects will receive the hospital/institutions and surgeons standard pre-operative and post-operative care with the addition of any study specific requirements.

All subjects will have total blood loss recorded at the completion time of surgery as per standard of care.

Either during or immediately post-operatively, the details of the SLNB procedure and surgical procedure will be documented. LN mapping data will be collected including the ability to visualize lymphatic vessels and identify LNs as well as data to confirm the safety of intradermal injection of IC2000. In subjects in whom lymphatic flow through the lymphatic vessels may be occluded or damaged proceed to alternate route of administration of IC2000 and map with SPY.

Failed mapping is defined as no LNs detected by either Tc99m and Gamma Probe, IC2000 and SPY or LNs deemed clinically suspicious.

LNs identified during the mapping procedure will be classified according to Section 7.4, Classification of LNs, and recorded in the CRFs.

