12.5 Histopathology of Excised LN

The presence of lymphoid tissue for each excised LN will be confirmed by tissue analysis.

All LNs will be routinely sectioned and stained with pathology assessment as per the hospital/institutions standard procedure.

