13.5 Reporting of Technical Complaints / Device Deficiencies

13.6 ADEs Technical Complaints / Device Deficiencies that are UADEs

14. STATISTICAL CONSIDERATIONS

14.1 Analysis PopulationsPer-protocol (PP)

Since this is a non-inferiority design, the PP analysis population will be primary; it will comprise all subjects that: (1) meet all eligibility criteria; (2) received the full dose of tracer / dye; (3) successfully completed the mapping procedure (i.e. have at least one lymph nodes detected *in-vivo* by IC2000 and SPY or by Tc99m and Gamma Probe, or have lymph nodes deemed clinically suspicious), and; (4) have histology confirmed lymph nodes.

Modified Intent to treat (mITT)

The mITT analysis population will comprise all enrolled subjects who received at least one injection of IC2000 and Tc99. All subjects meeting this criterion will be included in the mITT population regardless of whether or not (1) they received lymphatic mapping (i.e. they only had LNs identified through palpation), or (2) received the full dose of tracer / dye. Subjects who have the mapping procedure aborted due to circumstances, such as a higher stage cancer than initially expected, subjects with failed mapping, or subjects without histology confirmed lymph nodes will not be included in the mITT. The mITT population will be used for a secondary analysis of the primary endpoint.

Safety

The safety analysis population will comprise all subjects enrolled in the study who received at least one injection of IC2000 regardless of whether LN mapping was initiated or was successful. All safety endpoints, including the summary of AEs or ADEs in the trial, will be analyzed using this analysis population.

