14.3 Primary Objective

To assess the effectiveness of IC2000/SPY during lymphatic mapping and sentinel lymph node biopsy, the proportion of excised lymph nodes identified by IC2000/SPY in-vivo and confirmed by histology (\mathbf{Q}_{T}) will be compared with the proportion of excised lymph nodes identified with Tc99m/Gamma and confirmed by histology (\mathbf{Q}_{C}). The denominator for both \mathbf{Q}_{T} and \mathbf{Q}_{C} will be the total number of lymph nodes identified and excised that were confirmed by histology, inclusive of clinically suspicious lymph nodes.

The following hypothesis will be tested at the lymph node level:

H0:
$$Q_T \le Q_C - 0.05$$
 H1: $Q_T > Q_C - 0.05$

To test this hypothesis, the difference \mathbf{Q}_{T} - \mathbf{Q}_{C} will be calculated and the associated two-sided 95% confidence interval. If the lower bound of the interval is greater than -0.05, non-inferiority (using the PP population) will be claimed.

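### Could a metastatic node found on histology remove a subject from the primary per-protocol population?

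*Combined protocol and SAP*

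**What the plan says.** - **Entry.** Section 8.2 requires every criterion to be met. One bullet lists the permitted stages and calls them clinical stages. Another admits "Subjects with clinically negative nodal status (N0) with or without neoadjuvant therapy". The line defining N0 as absence of regional nodal metastasis belongs to the legend under the stage bullet.
- **Timing of the check.** Section 7.2 has subjects assessed against the criteria at baseline. Section 9.1 states: "Prior to surgery, the subject will have provided written informed consent, completed all baseline procedures and met all the requirements of inclusion and exclusion". Section 12.3 places enrolment "just prior to the time of injection of IC2000, at the start of surgery".
- **After enrolment.** Section 9.1.1: "If, at any time after enrollment, the subject becomes ineligible or withdraws, the subject will be categorized with respect to the definitions outlined", which sends the reader to Section 14.
- **Primary population.** Section 14.1 lists four PP conditions: that subjects "1) meet all eligibility criteria", had the full dose, completed mapping, and have histology-confirmed lymph nodes. Section 14.3: "If the lower bound of the interval is greater than -0.05, non-inferiority (using the PP population) will be claimed".
- **Secondary population.** The mITT population has no eligibility condition. It leaves out, among others, "Subjects who have the mapping procedure aborted due to circumstances, such as a higher stage cancer than initially expected".
- **Histology.** Section 12.5: "All LNs will be routinely sectioned and stained with pathology assessment". The same section has tissue analysis confirm that each specimen contains lymphoid tissue.

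**The concern.** The eligibility condition in Section 14.1 is undated, while conditions (3) and (4) in the same sentence depend on what happens during and after surgery. Section 9.1.1 expects that a subject can become ineligible later and refers to definitions that do not say how to treat one whose mapping was completed and whose node then proves metastatic. Section 14.1 mentions unexpectedly high stage only for mITT, and only where mapping was aborted.

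Taken literally, that allows three treatments of a subject who was N0 at baseline:

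- (a) Eligibility is fixed at enrolment and the subject stays.
- (b) The stage list is re-read after histology. A T1 subject stays, because T1 with N1 or N1mi is listed. Tis and T2 subjects leave.
- (c) The N0 line is re-read after histology and all such subjects leave.

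Under (b) or (c), histology of the very nodes being compared would decide who is analysed, in an open-label study where the investigator has already classified each node by method. If the two methods compare differently in subjects with metastatic nodes, the quantity tested would shift, and the claim would not cover subjects in whom the biopsy found disease.

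**Working it through.** **1. The plan's own figure.** Inputs from Section 14.8: expected difference 0.044, discordance 0.112, margin 0.05, one-sided alpha 0.025, power 90%.

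- Wald formula: n = (1.960 + 1.282)² × (0.112 - 0.044²) / (0.044 + 0.05)² = 131.
- At the plan's n = 137 the same formula gives power 91.3%. Simulation gives 92.5% without and 88.2% with a continuity correction, which brackets the stated 90%.
- 137 × 2 = 274; 274 × 1.3 = 356; 356 / 0.94 = 379.

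Fixing the date of the eligibility check alters none of these.

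**2. Which reading the text supports.**

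| Text | Points to |
|---|---|
| 8.2: stage list headed as clinical stage; 5 words later tied to Tis, T1, T2 legend entries | (a) |
| 8.2: nodal line limited to clinical status | (a) |
| 7.2 and 9.1: assessed at baseline, met before surgery | (a) |
| 12.3: eligibility verified before IC2000 injection | (a) |
| 14.1, PP condition (4): asks whether the specimen is a lymph node | neutral; does not use metastatic status |
| 9.1.1: ineligibility after enrolment | open; no event named |
| 8.3: stage exclusion not labelled clinical | open; stage IIB is not defined in the documents |

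Readings (b) and (c) need a clinical criterion to be turned into a pathological one. The example of later change in Section 8.4 is a modified surgical procedure. The case of mapping aborted for higher stage would ordinarily fail PP condition (3) anyway.

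**3. What would follow if (b) or (c) were used.** Let s be the share of nodes removed and g the paired difference in kept nodes minus that in removed nodes. Set the true difference over all mapped nodes at -0.05, so that the claim rate should be 2.5%. Discordance is held at 0.112 in kept nodes.

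- Difference in kept nodes: d = -0.05 + s × g.
- P(claim) = Φ( (d + 0.05) / √[(0.112 - d²) / (n(1 - s))] - 1.96 ).
- Worked case, s = 0.2, g = 0.10, n = 137: d = -0.03; standard error = √(0.1111 / 109.6) = 0.0318; 0.02 / 0.0318 = 0.628; Φ(-1.332) = 0.092.

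| g | s = 0.1 | s = 0.2 | s = 0.3 |
|---|---|---|---|
| 0.10, n = 137 | 5.2% | 9.2% | 14.0% |
| 0.10, n = 274 | 6.9% | 14.2% | 23.7% |
| 0.05, n = 137 | 3.7% | 5.0% | 6.4% |
| 0.05, n = 274 | 4.2% | 6.5% | 9.1% |
| 0, either n | 2.5% | 2.5% | 2.5% |
| -0.05, n = 137 | 1.7% | 1.1% | 0.8% |
| -0.05, n = 274 | 1.4% | 0.8% | 0.5% |

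Here 274 is the effective number of pairs, 356 / 1.3. Both s and g are assumptions. Section 14.8 allows 6% PP exclusion for all causes together, so every column exceeds the plan's own allowance. At s = 0.06 and g = 0.10, d = -0.044 and the formula gives 4.0% (n = 137) or 4.7% (n = 274).

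**4. Whether mITT would reveal it.** Both populations require completed mapping and histology-confirmed nodes. In substance they differ only by PP conditions (1) and (2), eligibility and full dose, so any removal on eligibility would appear as a difference between the two analyses.

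**The case for a change.** The best case for acting is that Sections 7.2 and 9.1 govern entry, not membership of an analysis population. Section 9.1.1 plainly expects ineligibility to arise later, and Section 14.1 gives it no rule. The choice could decide the trial. With 356 nodes and inflation 1.3, suppose the observed difference is 0 in node-negative subjects and -0.10 in the 20% with metastatic nodes. Kept, the overall difference is -0.02 and the lower bound is -0.02 - 1.96 × √(0.1116 / 273.8) = -0.060, which fails. Dropped, it is 0 - 1.96 × √(0.112 / 219.1) = -0.044, which passes. The mITT analysis is secondary and cannot block the claim, and a dated criterion would cost one sentence.

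The arithmetic stands, and so does the statement that condition (1) is undated. What does not stand is the step to three equally live readings, because two of them contradict the clinical wording of the criteria. The illustration also needs a detection gap by nodal metastasis for which the documents give no evidence in either direction. With a difference of 0 in both groups the bounds are -0.040 kept and -0.044 dropped, and the conclusion is the same.

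Section 8.2 also names N1 and N1mi stages beside the N0 line. The two lines could be worded more consistently, but since all criteria must be met, tidying them changes no entry decision.

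**Conclusion.** No change to the plan is needed. The eligibility condition lacks an explicit date, but the criteria are clinical, they are judged at baseline and before surgery, and no visible PP rule turns on metastatic status. An analyst following the plan would keep a subject whose mapping was completed and whose node proved metastatic, and that gives a sound primary analysis. A departure would show against the prespecified mITT analysis.

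No inflation of the error rate is shown from the documents. The figures of 9% and 14% in place of 2.5% require a departure from the ordinary reading, a loss of 20% of nodes against a 6% allowance for all causes, and a 10-point gap of assumed size and direction. Requiring mITT to pass as well would be a trade-off, not a correction.

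This rests on the visible text. Sections 14.5, 14.7 and 18 show no content in the public copy and may already settle the point.
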